8.2.3. Sensitivity Analyses of the Primary Analysis

Sensitivity analyses of the primary efficacy endpoint will be conducted to evaluate the robustness of study results under different assumptions and imputation algorithms. For the primary endpoint, categorized as absolute SALT score ≤ 20 at Week 24, the following sensitivity analyses will be performed for the Efficacy Population only.

Sensitivity 1: Multiple imputation; missing not at random (MNAR)

This sensitivity analysis is an implementation of a pattern mixture model that draws from different populations based on the reason for withdrawal from study. Patients who discontinued the study early due to a treatment-emergent adverse event (including COVID-19) or due to lack of efficacy will be considered MNAR. Treatment-emergent adverse event and lack of efficacy are reasons collected under “If 'Withdrew Consent', specify reason” on the *Study Discontinuation/Completion eCRF* page.

For patients who discontinued the study early due to a treatment-emergent adverse event or lack of efficacy, SALT scores missing after discontinuation will be imputed using the control arm. This assumes that patients, regardless of treatment, who discontinue the study early for those reasons would have similar SALT scores to placebo patients with complete data.

For patients who discontinued the study due to reasons other than treatment-emergent adverse event or lack of efficacy, missing SALT scores after subjects discontinue the study early will be multiply imputed from subjects within the same treatment group who have complete data at that time. Terms will include baseline values and the weekly data through the time point being imputed.

The proportion of patients who have a SALT score ≤ 20 will be calculated for each imputed dataset. The primary analysis, as described in Section 8.2.2, will be repeated for the Efficacy Population using the MI with MNAR assumption datasets.

Sensitivity 2: Tipping point

Additionally, a tipping point sensitivity analysis will be conducted for each dose compared to placebo at Week 24 if the result of the MI analysis is statistically significant at the alpha ≤ 0.025 level, in favor of treatment, for the given dose. The tipping point analysis will use the primary MAR assumption datasets, where all imputed values are adjusted.

The tipping point analysis will apply delta adjustments for both treated and placebo. For the tipping point analyses, δ_T values (adjustments for treated patients) will represent a percentage difference between the imputed value and baseline and can vary from 0% to 100% of the difference for subjects with an imputed SALT score less than baseline, or zero otherwise. For the placebo arm, δ_P values will represent a percentage difference between the imputed value and 0 hair loss. Accordingly, the maximum delta value of 100% provides for an adjusted imputed value equal to either baseline (for treated subjects, representing non-response) or zero hair loss for placebo, representing response. Tipping points will therefore be provided for combinations of δ_T and δ_P to provide a range of assumptions about hypothetical improvements on placebo missing

data values and reduction in efficacy for treated imputed values such that there is no longer evidence of efficacy.

[figure not shown]
8.2.4. Secondary Analyses of the Primary Endpoint

No secondary analyses specified.

8.3. Key Secondary Endpoints

See Section 8.1.4 and Figure 1 below for hierarchical testing.

Figure 1: Hierarchical Testing

8.3.1. Hair Satisfaction Patient Reported Outcome (SPRO) at Week 24

The first key secondary endpoint is the percentage of responders per the SPRO at Week 24. The SPRO is a single item questionnaire answered by the patient, designed to measure how satisfied alopecia areata patients are with their hair at the time of the assessment. The SPRO responses are on a scale of 1-5, where 1 = very satisfied, 2 = satisfied, 3 = neither satisfied nor dissatisfied, 4 = dissatisfied, and 5 = very dissatisfied. An example of the SPRO assessment can be found in Appendix 17.4.1 of the protocol.

A responder is defined as patients with answers of “very satisfied” or “satisfied” at Week 24 on the SPRO. This endpoint will be assessed similar to the primary analysis for the primary endpoint, according to Section [8.2.2](#).

Missing data will be imputed similarly to the primary endpoint according to Section [8.2.1](#). However, since the SPRO scale is ordinal, the FCS logistic regression method will be used in lieu of the FCS regression method. The missing SPRO scores will be imputed in a sequential manner using logistic regression models with baseline SALT score, baseline SPRO score, and the observed or imputed SPRO values of previous visits as covariates.

The observed number and percentage of SPRO responders by treatment group will be reported along with the appropriate p-values. Both CTP-543 doses will be tested in parallel against placebo with a ≤ 0.025 alpha level. This analysis will be completed for the Efficacy Population and the Per Protocol Population. The Per Protocol Population will be considered supportive. If the primary endpoint is unsuccessful, nominal p-values will be reported.

8.3.2. SALT Score ≤ 20 at Weeks 20, 16, 12, and 8

The next key secondary endpoints are the percentage of patients achieving an absolute SALT score of ≤ 20 (i.e., the binary endpoint denoting a SALT score ≤ 20) at Weeks 20, 16, 12, and 8. Missing data will be imputed according to Section [8.2.1](#). These endpoints will be assessed according to Section [8.2.2](#). If the primary endpoint and first key secondary endpoint are unsuccessful, nominal p-values for the SALT key secondary endpoints will be reported. This analysis will be completed for the Efficacy Population and the Per Protocol Population. The Per Protocol Population will be considered supportive.

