Patients will take the first dose of study drug in the clinic on Day 1 and will be instructed to take study drug daily approximately every 12 hours for the duration of the Treatment Period. Patients should dose study drug in the clinic on all Study Visit Days after clinical laboratory blood draws are completed. Other baseline assessments will include patient and clinician global impression of disease severity (CGI-S and PGI-S), Patient Reported Outcome for Satisfaction (SPRO) and Hair Quality (QPRO), the Hospital Anxiety and Depression Scale (HADS), and assessments for eyelash and eyebrow involvement.

The double-blind, placebo-controlled Treatment Period will last 24 weeks. Assessment of treatment response using SALT for efficacy will occur at 4, 8, 12, 16, 20 and 24 weeks.

Patient safety will be monitored throughout the trial by the Investigator and supported by regular review by the Medical Monitor and DMC. Chemistry and hematology laboratory values will be assessed under fasted conditions bi-weekly for the first month of the treatment period, followed by every 4 weeks through the remainder of the study. Lipid levels will be assessed every 4 weeks throughout the Treatment Period. In light of the COVID-19 pandemic, challenges in the conduct of study visits may arise from quarantines, site closures, and/or travel limitations. To ensure the safety of trial participants and to minimize risk to trial integrity, alternative methods for drug dispensation and assessments, including telemedicine visits and clinical laboratory blood draws at a local laboratory or via a Home Health Care agency, may be offered for those trial participants who may no longer have access to the investigational site. Significant cytopenias or other hematologic abnormalities will be managed by severity through dose interruption or discontinuation, and signs and symptoms of infection will be closely monitored and treated promptly. Patients who experience intolerable symptoms during treatment may discontinue treatment at the judgement of the Investigator, but will be followed for safety and efficacy assessments until Week 24, unless they withdraw consent. Patients may withdraw consent at any time.

Following the 24-week Treatment Period, patients will have the opportunity to continue receiving treatment in an Open-Label Extension study. If a patient does not wish to continue into the Open-label

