Patient Reported Outcome Scales: SPRO and QPRO		X		X ¹²	X	X	
Patient and Clinical Global Impression of Improvement (PGI-I, CGI-I ¹¹)				X ¹²	X	X	
Patient and Clinical Global Impression of Severity (PGI-S, CGI-S ¹¹)		X		X ¹²	X	X	
Hospital Anxiety and Depression Scale (HADS)		X				X	
Dispense study drug ¹³		X		X	X		
Study drug accountability				X	X	X	
Adverse events ¹⁴	X	X	X	X	X	X	X
Concomitant medications ¹⁴	X	X	X	X	X	X	X

HBV = hepatitis B virus; HCV = hepatitis C virus
 
¹ Due to the COVID-19 pandemic, patient study visits may be performed remotely when the provider and patient are not able to be physically present in the clinic. Study personnel should strive to perform assessments per the schedule of events above with the understanding that all assessments may not be able to be performed (ECGs, vitals, SALT assessments).
 
² Randomization/Day 1 may occur any time after eligibility has been confirmed.
 
³ All subsequent visits and week increments should be based on the date of Visit 2 (Day 1).
 
⁴ All visit windows are ± 2 days.
 
⁵ The Safety Follow-Up Visit is intended for those patients who do not roll over into the Open-Label Extension.
	
⁶ Serum pregnancy test only for females of childbearing potential
 
⁷ Includes hematology, serum chemistry, and lipids (fasted) performed by the central lab.
 
⁸ Collected pre-dose.
 
⁹ Will include thyroid stimulating hormone and hemoglobin A1c at Screening only.
 
¹⁰ Will include hematology and serum chemistry only.
 
¹¹ Should be performed by the same rater for the patient for the duration of the study.
 
¹² Performed at Week 12 only.
 
¹³ Due to COVID-19, Direct to Patient (DTP) shipping services may be warranted in cases where a patient is not able to attend in clinic visits or a site is closed.
 
¹⁴ Collection is ongoing.

---	---

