8.1.4. Multiple Comparisons/Multiplicity

Hierarchical testing will be used to control for multiple comparisons (Figure 1). For the primary efficacy analysis and the key secondary efficacy analyses, a ≤ 0.025 (two-sided) alpha-level will be allocated to each dose for comparison with placebo to adjust for multiplicity of testing associated with two doses. Once $p>0.025$ is observed for a treatment group comparison, inference for additional endpoints is no longer alpha-level protected for that dose group; however, nominal p-values will still be reported.

Subsequently, conditional upon significance (≤ 0.025) for the primary endpoint and first key secondary endpoint for each dose, a linear hierarchical testing approach with ≤ 0.025 (two-sided) alpha-level will be used to test the remaining key secondary endpoint comparisons versus placebo. Once $p>0.025$ is observed for a treatment group comparison, inference for additional endpoints is no longer alpha-level protected for that dose group; however, nominal p-values will still be reported.

All other statistical tests outside of the hierarchy will be carried out at a two-sided significance level of ≤ 0.05 . Nominal p-values will be presented without adjustment for multiple comparisons.

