8.2.1. Computation of the Primary Endpoint

The SALT is a measure of hair loss that quantifies the amount of scalp surface without hair in a pre-specified quadrant of the scalp (right side, top, left side, back), that is further summed after applying a quadrant-specific multiplier indicative of scalp surface area contribution, to provide an overall score of total hair loss. A total SALT score equal to 0% indicates complete hair growth. A total SALT score equal to 100% indicates complete hair loss. An example of the SALT assessment can be found in Appendix 17.2 of protocol. The overall total SALT score is calculated in the eCOA system and will not re-derived. SALT scores are considered missing if the overall total could not be calculated.

The primary endpoint is derived by categorizing the individual overall SALT scores at Week 24 (≤ 20 versus > 20).

A multiple imputation (MI) approach will be used to estimate missing SALT scores.

One hundred independent imputations will be done with SAS® PROC MI using the Fully Conditional Specification (FCS) regression method. The FCS method combines both the monotone and arbitrary missing data patterns into one procedure, imputing missing values with a sequential regression approach.

For the primary efficacy analysis, missing SALT scores will be imputed under a missing at random (MAR) assumption. This assumes that patients who have missing data would have similar SALT scores as other patients in their respective treatment arm who have complete data. Any missing post-baseline SALT scores will be imputed to better inform the estimates of Week 24 missing SALT scores. Patients who have discontinued treatment but remain on study will not have their SALT scores censored, but any arbitrary missing SALT scores after the patient discontinued treatment will be imputed in the same manner. Utilizing the FCS method, missing SALT scores will be imputed in a sequential manner using regression models with baseline SALT score and the observed or imputed values of previous visits as covariates. Imputations will be implemented separately for each treatment under the assumption that different treatments may have distinct posterior distributions.

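### Missing Week 24 SPRO is imputed without any post-baseline SALT, so patients lost before Week 12 are imputed from arm and baseline values alone; adding Week 4 and Week 8 SALT is a cheap improvement

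*SAP*

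**What the plan says.** SAP 8.3.1 sets the endpoint: "The first key secondary endpoint is the percentage of responders per the SPRO at Week 24". Under SAP 8.1.4, "a ≤ 0.025 (two-sided) alpha-level will be allocated to each dose for comparison with placebo", and SPRO has to be passed before the SALT key secondaries at Weeks 20, 16, 12 and 8 are alpha-protected.

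For missing SPRO, SAP 8.3.1 points to the method of 8.2.1 and replaces the linear FCS step with an FCS logistic one, "using logistic regression models with baseline SALT score, baseline SPRO score, and the observed or imputed SPRO values of previous visits as covariates". No post-baseline SALT appears in that list. Two features carry over from 8.2.1. One is imputation by arm: "Imputations will be implemented separately for each treatment under the assumption that different treatments may have distinct posterior distributions". The other is a missing-at-random premise, stated there for SALT, that "patients who have missing data would have similar SALT scores as other patients in their respective treatment arm who have complete data".

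In Protocol Table 2 the row "Patient Reported Outcome Scales: SPRO and QPRO" is marked in the joint column for Weeks 4, 8 and 12 with footnote 12, "Performed at Week 12 only". SPRO is thus scheduled at Baseline and Weeks 12, 16, 20 and 24 or early termination. SALT starts sooner: "Assessment of treatment response using SALT for efficacy will occur at 4, 8, 12, 16, 20 and 24 weeks" (Protocol synopsis).

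Three further places matter:
- SAP 8.1.2 lets early-termination data move only to a visit at which that assessment is scheduled. The Week 12 efficacy window is Days 82-88.
- SAP 8.2.3 plans missing-data sensitivity analyses for the primary endpoint only.
- SAP 13 explains that SPRO is imputed so that its handling matches that of the other alpha-controlled endpoints.

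**The concern.** SPRO asks how satisfied the patient is with the scalp hair, so early SALT is an obvious predictor of it. For a patient lost before Week 12 the imputation model holds only baseline SALT and baseline SPRO, within arm. SPRO taken at an early-termination visit before Day 82 does not help, because the windows give it no analysis visit. Week 4 and Week 8 SALT may show no regrowth at all, yet the model cannot see it.

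If patients leave because they see no regrowth, missing at random given baseline alone is hard to defend. Non-regrowers on active drug would then be given the satisfaction rate of patients who stayed. The plan itself treats this kind of dropout as possible: Sensitivity 1 in SAP 8.2.3 handles study discontinuation for lack of efficacy as missing not at random, but only for the primary endpoint. The SALT endpoints do use early SALT in their imputation, so the alignment sought in SAP 13 is only partly achieved. At stake is the estimate for the endpoint that gates the remaining key secondaries.

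**Working it through.** **1. The plan's own figure.** Protocol 12.1 gives SALT response of 40%, 25% and 10% with 210, 350 and 140 patients (12 mg, 8 mg, placebo), two-sided alpha 0.025 (critical value 2.24). For 8 mg v placebo:
- pooled rate = (350 × 0.25 + 140 × 0.10)/490 = 0.207
- null SE = √(0.207 × 0.793 × (1/140 + 1/350)) = 0.0405
- alternative SE = √(0.25 × 0.75/350 + 0.10 × 0.90/140) = 0.0343
- power = Φ((0.15 − 2.24 × 0.0405)/0.0343) = 95.8%, or 94.3% with continuity correction, against about 94% stated. The 12 mg comparison exceeds 99%, as stated.

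The power statement is unaffected by this point. The documents give no response rate, power or dropout figure for SPRO, so the 40/25/10% rates serve below as a proxy.

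**2. Formula for the shift.** With early dropout d in each arm, shift in the difference = d × (imputed − true response of dropouts) on active, minus the same on placebo. If active dropouts truly respond at the 10% placebo rate but are imputed at the arm average, and placebo is unbiased, the shift is d × (arm rate − 0.10). For d = 3, 5 and 10% this is 0.9, 1.5 and 3.0 points (12 mg) and 0.45, 0.75 and 1.5 points (8 mg).

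**3. Simulation, 300,000 patients per arm.** Assumptions, none from the documents except the proxy rates:
- Baseline SALT and baseline SPRO correlate weakly (0.3 and 0.1 in size) with a latent Week 24 satisfaction score.
- Week 8 SALT improvement correlates 0.4, 0.6 or 0.8 with the part of that score not explained by baseline.
- The log-odds of dropout before Week 12 fall by 1.2 per SD of Week 8 improvement.
- Dropout is equal across arms.
- Response is imputed by a binary logistic model fitted by arm, once with the SAP covariates and once with Week 4 and Week 8 SALT added.

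Results with the SAP covariates (true and imputed response among dropouts in %, shift in points):

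| Correlation | Dropout | 12 mg true / imputed | Shift | 8 mg true / imputed | Shift |
|---|---|---|---|---|---|
| 0.4 | 3% | 24.9 / 40.7 | 0.31 | 13.3 / 25.2 | 0.19 |
| 0.4 | 5% | 25.1 / 40.6 | 0.48 | 14.0 / 25.7 | 0.30 |
| 0.4 | 10% | 27.1 / 41.4 | 0.85 | 14.7 / 26.1 | 0.57 |
| 0.6 | 3% | 18.2 / 40.5 | 0.44 | 8.9 / 25.2 | 0.26 |
| 0.6 | 5% | 19.1 / 40.9 | 0.72 | 9.8 / 25.9 | 0.43 |
| 0.6 | 10% | 20.9 / 42.2 | 1.38 | 10.6 / 26.5 | 0.83 |
| 0.8 | 3% | 13.1 / 40.8 | 0.58 | 6.1 / 25.5 | 0.33 |
| 0.8 | 5% | 14.0 / 41.3 | 0.91 | 6.4 / 26.1 | 0.54 |
| 0.8 | 10% | 15.4 / 42.8 | 1.82 | 7.5 / 27.0 | 1.05 |

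The row at 0.6 and 5% agrees with step 2. The 12 mg arm rate is too high by 0.05 × (40.9 − 19.1) = 1.09 points. The shift of 0.72 implies about 0.37 on placebo.

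With Week 4 and Week 8 SALT added, the shift is 0.1 point or less in size in every row. That is expected, since simulated dropout depends on Week 8 SALT and every dropout has it observed.

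**4. Unequal dropout, correlation 0.6.** With 10% on active and 3% on placebo, +1.91 (12 mg) and +1.36 (8 mg). With 3% on active and 10% on placebo, −0.08 and −0.29. With no true effect (10% response in both arms), equal dropout gives 0, and 10% v 3% gives +0.52.

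**5. Against the standard error.** SE of the difference at the proxy rates: 12 mg √(0.40 × 0.60/210 + 0.10 × 0.90/140) = 4.23 points; 8 mg 3.43 points. Z = 30/4.23 = 7.1 and 15/3.43 = 4.4. Taking off the largest simulated shifts gives (30 − 1.9)/4.23 = 6.6 and (15 − 1.4)/3.43 = 4.0. The harsher step 2 case at 10% gives (30 − 3.0)/4.23 = 6.4 and (15 − 1.5)/3.43 = 3.9. All stay well above 2.24.

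**The case against.** **The bias is assumed, not shown.** The simulation makes dropout depend on the variable left out, so bias must follow. Nothing in the documents says how many patients leave early or why. This stands: if dropout is unrelated to regrowth, only precision is lost.

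**Few patients are affected.** Protocol 8.3 keeps patients who stop drug in follow-up with all endpoints collected. Protocol 10.5 moves SPRO to video when COVID-19 prevents a visit. Anyone with SPRO at Week 12, 16 or 20 is imputed from that score. This also stands, and it argues for the low end of the dropout range.

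**The model mirrors the SALT model.** Each uses baseline plus the endpoint's own history, a fair reading of alignment. But SALT history begins at Week 4 and SPRO history at Week 12, so the same form leaves SPRO with less information. The general FCS wording in Protocol 12.4.5, in which all other variables serve as covariates, does not settle the matter: SAP 2 gives the SAP primacy, and SAP 8.3.1 lists its covariates.

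**Stronger readings that the documents do not support.** A reader might infer that early dropouts are imputed simply at the arm average. They are imputed conditionally on baseline SALT and SPRO, although in the simulation this moved the 12 mg rate only to 40.5-42.8% against 40%. A reader might also infer that the bias always favours the drug, but more dropout on placebo makes it slightly negative. Nor is the gate's error control shown to fail. With no true effect and equal dropout the shift is zero. With 10% v 3% it is 0.52 point, or 0.16 SE for 12 mg (null SE √(0.09/210 + 0.09/140) = 3.27 points).

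**Conclusion.** The point holds as a gap in the imputation model with a cheap remedy. It is not evidence that the SPRO test is invalid. The covariate list, visit schedule and analysis windows together mean that early SALT cannot inform the SPRO imputation, and no planned SPRO sensitivity analysis would show the effect.

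The size is modest and conditional. The equal-dropout overstatements, at most 1.82 and 1.05 points, are about 0.43 and 0.31 of a standard error (1.82/4.23 and 1.05/3.43). They rest on the proxy response rates, the assumed dropout and the assumed link to regrowth. Lower SPRO response rates than the proxy could leave less margin at the gate, but the documents give none.

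**What to change.** Before database lock, amend SAP 8.3.1 so that the SPRO imputation model, fitted by arm, also includes observed or imputed post-baseline SALT: at least Week 4 and Week 8 SALT, plus SALT at the visit being imputed. Imputing SALT and SPRO jointly in one FCS step would serve equally well. Pre-specify a reduced set, for example the most recent SALT only, for use if the ordinal model does not converge or separates.

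The cost is SAP wording and a few more variables in an existing PROC MI step; the data are already collected. The drawback is a heavier model in the placebo arm, where about 140 patients at a 10% proxy rate give some 14 responders for a five-category scale. That is why all six SALT visits should not be added by default. The change does nothing for patients lost before Week 4, and helps less for those lost between Weeks 4 and 8, who have one early SALT score instead of two.

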8.4. Secondary Endpoints

All statistical tests outside of the hierarchy defined in Section [8.1.4](#) and Figure 1 will be carried out at a two-sided significance level of ≤ 0.05 . Nominal p-values will be presented. Analyses will be performed using the Efficacy Population.

Missing values will not be imputed for efficacy endpoints which are not derived from SALT or SPRO scores.

For the secondary endpoints of proportions of patients achieving specified improvement criteria (hereinafter, “secondary responder endpoints”), pairwise treatment group differences from placebo at each scheduled evaluation will be assessed with the Cochran-Mantel-Haenszel test using baseline scalp hair loss as the stratification factor. Observed counts and percentages of responders will be summarized by treatment group and the p-values reported. Secondary responder endpoints derived from SALT or SPRO scores will be analyzed similarly to the primary endpoint according to Section [8.2.2](#).

For the secondary endpoints of absolute or relative changes (hereinafter, “continuous secondary endpoints”), treatment differences will be assessed with a mixed-effect model of repeated measures (MMRM). Model covariates are described in applicable sections below. Treatment group comparisons at each visit will be based on least squares (LS) mean estimates. An unstructured covariance matrix will be used to model the within-subject errors. Should the model fail to converge, an alternative autoregressive covariance matrix will be used instead. The Kenward-Roger approximation will be used to estimate the denominator degrees of freedom. Assuming that the data are MAR, the estimates of the treatment differences calculated from the MMRM described above are unbiased. Standard descriptive statistics will be reported for each time point on the values and changes from baseline along with the LS means, standard errors, 95% CIs and differences between treatment groups reported with LS means, standard errors, and 95% CIs.

